## **14 QUALITY ASSURANCE AND QUALITY CONTROL**

### **14.1 Quality Assurance and Quality Control**

A regulatory inspection of this study may be carried out by regulatory agencies. Such audits/inspections can occur at any time during or after completion of the study. If an audit or inspection occurs, the PI and RPL agree to allow the auditor/inspector direct access to all relevant documents and to allocate their time and the time of their staff to the auditor/inspector to discuss any findings or relevant issues.

Quality Control (QC) procedures at the CPU will be implemented to ensure data recorded into the CRFs are accurate before CRFs are sent for data entry purposes. QC checks will be carried out on critical phases in the execution of the study. These control checks will be carried out according to the relevant SOPs. Records of these procedures will be documented and available for review.

### **14.2 Monitoring**

All aspects of the study will be carefully monitored by the sponsor, or designee, for compliance with applicable government regulations with respect to Good Clinical Practice (GCP) and current standard operating procedures.

The monitoring of this study will be performed by the Sponsor's Monitor(s) or a designee in accordance with the principles of GCP as laid out in the International Conference on Harmonisation (ICH) "Good Clinical Practice: Consolidated Guideline".

The clinical monitor, as a representative of the Sponsor, has an obligation to follow the study closely. In doing so, the monitor will visit the Investigator and site periodically as well as maintain frequent telephone and letter contact. The monitor will maintain current personal knowledge of the study through observation, review of study records and source

documentation, and discussion of the conduct of the study with the Investigator and staff. Further details will be described in the SOM.

## **15 STATISTICAL METHODS PLANNED AND DETERMINATION OF SAMPLE SIZE**

### **15.1 Statistical and Analytical Plans**

The analysis will be computed with SAS Version 9.4 (Copyright© 2013 by SAS Institute Inc., Cary, NC, USA).

The statistical analysis plan will be agreed by the sponsor.

Individual data listings will contain all available results. They will be presented by IMP (LR12 vs Placebo), dose group (Group 1-Group 8), subject number and time point if applicable.

Descriptive statistics will be presented by IMP and time point.

All relevant data will be summarised as follows:

- Quantitative endpoints will be presented in terms of mean, standard deviation, median, Q1, Q3, extreme values, number of subjects and missing data.
- Qualitative endpoints will be presented in terms of number and percentage of each modality and number of subjects and missing data.

For quantitative endpoints, Student test for parametric tests or Wilcoxon test for non-parametric tests will be used.

For qualitative endpoints, Chi-square test for parametric tests or Fisher Exact test for non-parametric tests will be used.

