#### **Pharmacokinetics:**

Individual and mean concentration versus time will be plotted on linear and semi logarithmic scales. Plasma concentrations and plasma PK parameters will be listed for LR12. Summary statistics of PK parameters including means, geometric means, medians, ranges, standard deviations, coefficients of variation will be presented for each dose.

Analysis of variance models will be applied to the dose normalised and logarithmically transformed pharmacokinetic parameters to investigate possible deviations from dose proportionality

---

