### **6.3 Rationale for Conducting Study**

The aim of this First-in-Human (FIH) study is to obtain information on the safety, tolerability and pharmacokinetics of single ascending doses of MOTREM in healthy young male subjects.

The rationale for taking MOTREM into further development is the expectation that this compound could be an effective new anti-sepsis therapeutic agent. Prior to initial testing in patients, the safety and the pharmacokinetic characteristics of the drug in healthy humans must be investigated.

Data from this study will help to design subsequent studies in patient populations clinically and therapeutically relevant with this new class of compound.

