### **7 STUDY OBJECTIVES**

#### **7.1 Primary Objectives**

- To assess the safety and tolerability of MOTREM in comparison with placebo, after single intravenous (i.v.) dose administration in healthy young male subjects.

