**Table 11. Daily dose of IMP (MOTREM or matching placebo) for each dose group.**

Dose group	i.v. loading dose T = 15'	Maintenance i.v. dose (mg/kg/h) T = 7h45'	Number of subjects
Group 1	1 mg	-	N = 1
		-	
Group 2	10 mg	-	N = 1
		-	
Group 3	0.5 mg/kg Placebo	0.03 mg/kg/h Placebo	N = 3 N = 1
Group 4	1 mg/kg Placebo	0.1 mg/kg/h Placebo	N = 3 N = 1
Group 5	2 mg/kg Placebo	0.3 mg/kg/h Placebo	N = 3 N = 1
Group 6	5 mg/kg Placebo	1 mg/kg/h Placebo	N = 3 N = 1
Group 7	5 mg/kg Placebo	3 mg/kg/h Placebo	N = 3 N = 1
Group 8	5 mg/kg Placebo	9 mg/kg/h Placebo	N = 3 N = 1

IMOTREM or placebo will be administered by a Research Physician and the details of dosing will be recorded in the CRF. The dosing will be verified by another member of the Investigator's staff.

The study drugs will be dispensed by the pharmacy staff at the clinical study site. The pharmacy staff will be responsible for assembly and labelling of dosing containers according to randomisation schedules and assigned dose level. The amount/ volume of study drug to be administered will be determined based on the assigned dose level for a particular cohort. The procedure for preparing the study drugs and the volume to be prepared for each individual subject dose will be detailed in a Pharmacy Worksheet.

Detailed instructions for dose administration will be included in the Study Operations Manual (SOM).

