### **15.2.2 Statistical Analysis on PK Parameters**

Serum concentrations will be listed and summarised by time point. The PK parameters will be listed for each subject and summarised for each treatment group using descriptive statistics (N - the number of subjects, arithmetic mean, SD - standard deviation, CV - coefficient of variation, geometric mean, median, minimum, maximum).

Analysis of variance models will be applied to the dose normalised and logarithmically transformed pharmacokinetic parameters to investigate possible deviations from dose proportionality.

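### Section 15.1 groups safety summaries by LR12 versus placebo without dose, so the end-of-study safety tables, read literally, pool a 70- to 102-fold Part B dose range

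*Combined protocol and SAP*

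**What the plan says.** Two adjacent sentences in section 15.1 set different groupings. For individual listings: "They will be presented by IMP (LR12 vs Placebo), dose group (Group 1-Group 8), subject number and time point if applicable". For summaries: "Descriptive statistics will be presented by IMP and time point". The first explains IMP as the contrast between LR12 and placebo and names dose group as a further factor. The second keeps IMP and drops dose group. The title of Table 11 keeps the same two ideas apart: "Daily dose of IMP (MOTREM or matching placebo) for each dose group".

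The safety text does not bring dose back. Section 15.1.3 and the matching synopsis paragraphs organise adverse events by system organ class and preferred term, and vital signs, ECG and laboratory data by visit or time.

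Pharmacokinetic parameters are handled differently. The synopsis ends its list of summary statistics with "coefficients of variation will be presented for each dose", and section 15.2.2 says "The PK parameters will be listed for each subject and summarised for each treatment group using descriptive statistics".

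Section 15.1 also refers to a further document: "The statistical analysis plan will be agreed by the sponsor". None of its text is in the document reviewed.

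**The concern.** The primary objective in section 7.1 is "To assess the safety and tolerability of MOTREM in comparison with placebo", and one pooled LR12 column beside placebo is a legitimate display for that. But section 6.3 gives the aim of the study as obtaining "information on the safety, tolerability and pharmacokinetics of single ascending doses of MOTREM in healthy young male subjects". A reader of an ascending-dose study expects the final safety tables to show whether events or mean changes rise with dose.

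As written, the plan requires dose-level summaries for a secondary objective (PK) and not for the primary one (safety). At stake is the visibility, in the tables used to plan later studies, of an effect that appears only at the higher doses. It would be diluted by the subjects on lower doses, and nothing in the table would say where it came from.

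**Working it through.** There is no power calculation or stated figure behind this rule, so the check is of the grouping text (set out above) and of what pooling does to an effect.

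**LR12 subjects in the pooled column**
- Part B: 6 groups × 3 = 18 (Table 11).
- Adding planned Part A: 18 + 2 = 20. With 6 placebo subjects this reproduces the planned total of 26 in section 9.1.
- Adding the extra Group 2 subject from Amendment 2: 21.

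**Dose range in one column**

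Total dose = loading dose + maintenance rate × 7.75 h. For Part B the ratio does not depend on body weight.
- Group 3: 0.5 + 0.03 × 7.75 = 0.7325 mg/kg (51.3 mg at 70 kg).
- Group 8 at 9 mg/kg/h: 5 + 69.75 = 74.75 mg/kg (5,232.5 mg). Ratio to Group 3: 102.
- Group 8 at Amendment 4's 6 mg/kg/h: 5 + 46.5 = 51.5 mg/kg (3,605 mg). Ratio to Group 3: 70.3.

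**Share of the top-dose effect left in the pooled mean or percentage**

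| Assumed pattern | n = 18 | n = 20 | n = 21 |
|---|---|---|---|
| One Part B group only (3/n) | 16.7% | 15.0% | 14.3% |
| Equal in Groups 6–8, none elsewhere (9/n) | 50.0% | 45.0% | 42.9% |
| Proportional to total dose, Group 8 at 9 mg/kg/h | 27.3% | 24.6% | 23.4% |
| Proportional to total dose, Group 8 at 6 mg/kg/h | 32.1% | 28.9% | 27.6% |

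The last two rows use (3 × sum of Part B doses + Part A doses) / (n × Group 8 dose), at 70 kg.
- Groups 3 to 7 are 51.3, 124.3, 302.8, 892.5 and 1,977.5 mg.
- The Part B sum is 8,580.8 mg, or 6,953.3 mg with the lower Group 8 rate.
- Part A adds 0 mg (n = 18), 11 mg (n = 20) or 21 mg (n = 21).
- Example for n = 18 at 9 mg/kg/h: 3 × 8,580.8 / (18 × 5,232.5) = 0.273.

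**Illustrations, with assumed effects**
- A mean change of 20 mmHg in Group 8 alone reads 20 × 3/n = 3.3, 3.0 or 2.9 mmHg in the LR12 column.
- An event in all 3 LR12 subjects of Group 8 and in nobody else reads 3/18, 3/20 or 3/21. The count of 3 is not diluted, but three events scattered over low doses give the identical row.

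**The case against.** The strongest reply is that the protocol's grouping phrases are shorthand. Section 15.2.2 says concentrations are summarised by time point and names no group at all, yet nobody would average concentrations over all doses. Section 15.1 does not say that its grouping is the only one, and table layout is normally settled in the statistical analysis plan. This stands in part: the unseen plan may already contain dose columns. It does not remove the point. Section 15.1 is not silent on grouping. It names one, directly after a sentence that names dose group separately.

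Other information also carries dose. Listings are sorted by dose group, and in a study of about 26 subjects they can be read through. Section 15.1 also asks for medians, quartiles and extreme values, so a large change in a few subjects would still be seen, though not attributed to dose. Section 8.2.2 requires a safety report for each cohort. These are real offsets. But listings give no means or percentages by dose, and the cohort reports are interim and initially blinded, with active and placebo subjects not separated.

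Three stronger readings are tempting and are not supported:
- **That the study cannot show a dose relation.** This is true only of the summary tables taken literally. The data and the listings retain dose.
- **That mild events escape group review, because Table 4 shows no action for Grade I.** The table is visibly broken in the extracted text and the empty cell may be a lost merged cell. Adverse events also go to the Safety Review Committee for each cohort.
- **That Part A is outside the Safety Set, because section 15.1.1 requires randomised subjects.** Section 9.5 specifies random assignment for Part B, but it opens by assigning subjects in the study by a randomisation schedule, and Table 2 has a randomisation row for Part A. The texts are mixed.

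**Conclusion.** The point holds for the wording of section 15.1 and the end-of-study safety tables that follow from it. Those tables would pool all LR12 doses. The 14–17% for an effect in one Part B group is less severe if the effect is shared by several groups or rises in proportion to dose (23–50% across the other patterns examined).

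The figures rest on planned cohort sizes, with 21 including the Amendment 2 subject, and on assumed effect patterns. Optional or extended cohorts would change them. They describe means and percentages, not extremes or counts.

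The consequence is limited: no data are lost, escalation decisions do not depend on these tables, and dose tables could be produced later from the same database. Confidence is high about the stated rule and lower about the tables finally produced, because the separate statistical analysis plan could not be seen. The correction is still worth making, since it is specific and almost free.

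**What to change.** In section 15.1, change the grouping for descriptive statistics to: *by LR12 dose group (each planned and any optional cohort, with Part A shown separately), all LR12 combined, and pooled Part B placebo, at each time point*. Apply it to the safety tables in section 15.1.3, carry it into the statistical analysis plan, and keep the display descriptive. The all-LR12 column continues to serve the comparison with placebo.

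The cost is wording and extra table columns; no further subjects or data are needed. The drawback is that each dose column holds only one to three LR12 subjects at planned size. One event in three reads as 33%, so show counts beside percentages and say that the percentages should not be over-read.

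As a minor separate clarification, define the Safety Set in section 15.1.1 by having been dosed with MOTREM or placebo, so that the place of Part A does not turn on the word randomised.

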#### **15.1.1 Data Sets Analysed**

Randomised set will comprise all randomised subjects.

Safety Set will include all randomised subjects who have taken the IMP, and who have at least one post-baseline assessment of safety, regardless any protocol deviations.

Per Protocol Set will include only the subjects who complete the study according to the protocol.

Subjects' assignment in different sets will be performed during the pre-analysis review meeting.

#### **15.1.2 Demographic and other Baseline Characteristics**

Analysis will be performed on the Safety Set.

Baseline characteristics such as demographic characteristics, subject's habits, toxicology, and serology, will be listed and summarised using descriptive statistics already mentioned.

Medical and surgical history, prior therapies will only be listed.

Previous medications will be coded according to the World Health Organization-Drug Reference List (WHO-DRUG dictionary version 2015-3) and will be listed.

Individual safety data (clinical laboratory, vital signs, and ECG) measured before the first drug administration will be checked for validity of entrance criteria, and abnormalities will be documented.

### **15.1.3 Safety analyses**

#### Adverse events:

Adverse events are coded using the MedDRA dictionary version 18.1 or higher. They are classified by System Organ Class and Preferred Term.

The number and percentage of subjects with at least one adverse event will be provided.

#### **Analysis of treatment-emergent adverse events (TEAE)**

Only TEAE will be summarised and described for the following criteria:

- Number and percentages of subjects with at least one TEAE
- Number and percentages of subjects with at least one severe TEAE
- Number and percentages of subjects with at least one study treatment related TEAE
- Number and percentages of subjects with at least one serious TEAE
- Number and percentages of subjects with at least one TEAE leading to treatment withdrawal

The maximum intensity encountered during the evaluation period will be checked.

The number of TEAE of each category will also be provided by system organ class and preferred term.

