##### **Analysis of treatment-emergent adverse events (TEAE)**

TEAEs will be summarised and described for the following criteria:

- Number and percentages of subjects with at least one TEAE
- Number and percentages of subjects with at least one severe TEAE
- Number and percentages of subjects with at least one study treatment related TEAE
- Number and percentages of subjects with at least one serious TEAE
- Number and percentages of subjects with at least one TEAE leading to treatment withdrawal

The maximum intensity encountered during the evaluation period will be recorded.

The number of TEAEs of each category will also be provided by system organ class and preferred term.

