## Study Plan

Single doses of MOTREM (LR12) or matching placebo (Part B) are planned to be administered following a sequential group design in 26 healthy young male subjects aged from 18 to 45 years: Part A (Groups 1 and 2 of 1 subject each) followed by Part B (Groups 3 to 8 of 4 subjects each). For Part A (Groups 1 and 2), one subject each will receive MOTREM. For Part B (Groups 3 to 8) 3 subjects will receive MOTREM and 1 subject will receive placebo (3:1 ratio). Dose escalation to the following scheduled dose will only occur after satisfactory review of all safety and tolerability data by the Safety Review Committee in accordance with Table 1, protocol sections [8.2](#) Rules for dose escalation/progression and [8.3](#) Toxicity rules.

Subjects will be screened within 14 days and may be performed over multiple days prior to entering the study on Day -1. Each subject will receive verbal and written information followed by signing of the Informed Consent Form (ICF) prior to any screening procedures taking place. Subjects will be admitted on Day -1 and on Day 1 of the study each subject will receive MOTREM (LR12). All the subjects from Part A (Groups 1 and 2) and Part B (groups 3 to 8) will be discharged on Day 2 after 24h post-dose (start of infusion). They will attend the unit for a follow-up visit on Day 8±1. The End of Study visit will take place on Day 28±2. All the assessments performed during the study are detailed in the Study Plan (Table 2 and Table 3). Study design features as well as number of subjects may be adapted according to Table 1.

The end of study is defined as the last subject, last visit (LSLV).

[figure not shown]

Figure 1: Study Flow Chart.

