**Reason for Amendment:**

1. The purpose of this amendment is to gather additional pharmacokinetic information. The amendment describes a 100% extension of Group 2 (Part A) in line with the Adaptive feature no 8, Limit I-III. Subject 202 will participate in Part A, group 2 and will be administered an intravenous MOTREM (LR12) dose of 10 mg over 15 min for further evaluation of the pharmacokinetic profile at the selected dose regimen. Three additional pre-dose blood samples will be obtained and processed in accordance with the Adaptive feature no 13 Limit I & II from the volunteer. These changes will not affect the volunteers' safety.

Inotrem SA considers this amendment to be non-substantial.

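### Read literally, the SOC and preferred-term tables give numbers of TEAEs rather than subjects; with 18 LR12 v 6 placebo subjects, about 3:1 is expected with no drug effect

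*Combined protocol and SAP*

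**What the plan says.** Section 15.1.3 lists five overall TEAE criteria: any, severe, treatment-related, serious, and leading to treatment withdrawal. Each is expressed in subjects; the first reads "Number and percentages of subjects with at least one TEAE". The section then turns to the breakdown: "The number of TEAE of each category will also be provided by system organ class and preferred term". The Study Synopsis (section 5) repeats this: "The number of TEAEs of each category will also be provided by system organ class and preferred term". Neither place states a subject count, percentage or denominator at SOC or preferred-term level.

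Two general rules in section 15.1 bear on the table. On columns: "Descriptive statistics will be presented by IMP and time point". On content: "Qualitative endpoints will be presented in terms of number and percentage of each modality and number of subjects and missing data". Section 15.1 also promises individual listings by IMP, dose group, subject and time point, and says that a statistical analysis plan will be agreed by the sponsor.

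On numbers, the Study Plan text in section 8.1 and Table 11 give Part B as six groups of four, three on MOTREM and one on placebo. Part A has no placebo: "For Part A (Groups 1 and 2), one subject each will receive MOTREM". Amendment 2 adds one more LR12 subject: "Subject 202 will participate in Part A, group 2".

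**The concern.** The primary objective is safety and tolerability in comparison with placebo. The risks named in sections 6.4.2.3 and 8.3 are specific reactions: hypersensitivity, anaphylaxis, and infusion or infusion-site reactions. The SOC and preferred-term table is where a difference in one of these would be read in the final report; the overall subject percentages do not show which reaction differs.

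An event count has two weaknesses there. Under 3:1 allocation the LR12 entry is expected to be about three times the placebo entry even if the drug does nothing. It also does not distinguish several affected subjects from one subject with repeated events. The second matters for local reactions in particular, because Table 3 schedules repeated infusion-site assessments in each Part B subject.

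**Working it through.** **Inputs.** Six Part B groups, each with 3 LR12 and 1 placebo subject (section 8.1, Table 11). Two planned Part A subjects, LR12 only (section 8.1). One further Group 2 subject on LR12 (Amendment 2). The same end-of-study visit for everyone, Day 28±2 (section 8.1). The documents give no TEAE rate, so the rates below are assumptions.

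**Step 1: reproduce the planned total.** LR12 in Part B: 6 × 3 = 18. Placebo: 6 × 1 = 6. Adding Part A: 18 + 6 + 2 = 26, which is the planned number in section 9.1.

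**Step 2: expected event ratio with no drug effect.** With a common rate r of events per subject and equal scheduled follow-up, expected counts are n × r in each arm, so the ratio is n(LR12)/n(placebo) whatever r is.

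- Part B only: 18/6 = 3.0
- With the two planned Part A subjects: 20/6 = 3.33
- With the extra Group 2 subject as well: 21/6 = 3.50

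Which applies depends on the Safety Set. Section 15.1.1 restricts it to randomised subjects. Section 9.5 describes random assignment for Part B only, but Table 2 also marks randomisation for Part A. Cohort extensions follow the original randomisation (Table 1), so they leave a 3:1 Part B cohort at 3:1.

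**Step 3: how often a single row would show the imbalance.** The ratio in step 2 is an expectation. Taking independent Poisson counts for 18 v 6 subjects with no drug effect:

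| Assumed events per subject | Expected LR12 v placebo | P(LR12 count higher) | P(tie) | P(LR12 count lower) |
|---|---|---|---|---|
| 0.05 | 0.9 v 0.3 | 0.49 | 0.39 | 0.12 |
| 0.2 | 3.6 v 1.2 | 0.81 | 0.11 | 0.08 |
| 0.5 | 9 v 3 | 0.95 | 0.03 | 0.03 |

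For a rare term, ties are common. For a frequent term or a whole SOC, the LR12 entry is nearly always the larger.

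**Step 4: what scaling recovers and what it does not.** Dividing each count by its arm size gives events per subject and removes the 3:1 artefact. It does not give subjects affected. Six LR12 events on one term could be six subjects with one event each, 6/18 = 33.3%, or one subject with six events, 1/18 = 5.6%. The table entry is 6 in both cases.

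**Step 5: the same table in subjects.** If a term affects one subject in three in both arms (assumed), the entries read 6/18 (33.3%) v 2/6 (33.3%). At one in six they read 3/18 v 1/6, 16.7% each. The gap due to allocation disappears without any scaling by the reader.

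**The case against.** The strongest case is that the wording is ambiguous and the harm small.

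- **The unit.** The categories referred to in the breakdown sentence are the five bullets above it, all defined in subjects, and the general rule for qualitative endpoints asks for numbers and percentages with the number of subjects. The sentence could therefore mean the same subject summaries, broken down by SOC and preferred term. This reading is possible, but the specific sentence names TEAEs directly after five lines that name subjects, and the general rule does not clearly override it. The ambiguity stands, and it is itself a reason to state the unit.
- **Deferred detail.** Section 15.1 refers to a statistical analysis plan still to be agreed, and table layouts may be settled there. That is fair, but the text available contains no other rule for this table.
- **Comparability.** A reader might infer that event counts leave the arms impossible to compare. The documents do not support that: arm sizes are known and scheduled follow-up is equal, so rates per subject can be derived. Subject-level listings would also let someone rebuild the counts by hand in a study of 26 planned subjects. What remains is that the table alone does not show how many subjects were affected.
- **Safety decisions.** A reader might also infer that dose escalation would rest on these counts. It would not. Table 4 in section 8.3 counts subjects affected, at grade II separately for the same and for different SOCs. Serious events also have their own table or listing.

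**Conclusion.** The point holds as a reporting weakness. As written, the plan most naturally gives event counts only at SOC and preferred-term level, in a comparison where about 3:1 is expected with no drug effect: 3.0 for Part B, 3.3 to 3.5 with Part A pooled. This assumes a common event rate, equal follow-up, and one LR12 column pooled over doses, as section 15.1 implies. It would be too strong to say that every row will show a threefold excess: for rare terms the observed counts vary widely, and at an assumed 0.05 events per subject the LR12 count exceeds placebo only about half the time.

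The loss that scaling does not repair is the number of subjects affected per term. The effect is limited to final descriptive tables, and neither subject safety during the trial nor the escalation decisions depend on it. It is best treated as a free improvement that brings the tables into line with the subject-based unit already used in Table 4.

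**What to change.** Replace the breakdown sentence in the synopsis and in section 15.1.3 with wording such as: *For each TEAE category, tables by SOC and preferred term will show the number and percentage of subjects affected (each subject counted once per SOC and once per preferred term), followed by the number of events; the column header will show the number of subjects in each group.*

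Event counts stay in the table, so nothing is lost. The cost is one sentence in two places plus table shells and programming. Data collection, randomisation and study procedures do not change.
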